7. DATA SAFETY AND MONITORING

Data Safety and Coordination

Data and safety monitoring, including guarding the rights, safety and welfare of subjects, will be the responsibility of the individual site investigators. The data coordinating center for the study will be the University of Alabama Birmingham (UAB). All information collected in this registry will be held confidential to the extent permitted by law. No published or unpublished report or visual or speaking presentation about this study will include any material that will identify the subject as a participant in this study. No specimens will be collected. Subjects may withdraw consent from the study at any time. Data will not be used by collaborators for any purposes other than those described in this protocol.

Data will be transferred to the coordinating center electronically for all data. Datasets containing de-identified individual data and summary data will be available to the INTERMACS and MedaMACS investigators and industry partners. All of the data systems feature multiple levels of security, which protect patient data by the most stringent requirements. All are fully compliant with the Health Insurance Portability and Accountability Act (HIPPA) and are certified by the Health Resources and Services Administration (HRSA). Any plans for data to be shared with outside entities as part of contractual arrangements will be within the conditions specified in the patient consent form and detailed in contracts to be reviewed separately.

Study Monitoring

The Principal Investigator and UAB study staff will regularly monitor the data from the registry, review and assess the performance of its operation, and make recommendations, as appropriate, to participating institutions with respect to:

- Enrollment and data timeliness and completeness from individual enrolling sites
- Issues related to participant safety and informed consents
- Adequacy of study progress in terms of recruitment, quality control, and data analysis
- Issues pertaining to participant burden
- Achievement on the main study goals
- Possible modifications in the study protocol
- Overall scientific direction of the registry

8. ANALYSIS PLAN

Planned Analysis

The prospective data analysis is planned to be descriptive and correlative, with primary hypothesis outlined in the specific aims. Data collected are designed to generate future hypotheses.

Actuarial survival curves will be generated and compared to known risk models, such as the Seattle Heart Failure Score and the Heart Failure Survival Score, for both heart failure populations and VAD populations from INTERMACS.^{19, 20} In addition, new models will be developed to allow comparison of anticipated outcomes after VADs using INTERMACS data. It is fully recognized that these comparisons will be inevitably limited through confounding by indication. The intent is to identify a range of baseline profiles for which anticipated outcome with medical survival can be projected. From this information, hypotheses can be generated for target populations in whom VAD therapy might be expected to yield better outcomes.

"Primary" Endpoint and Power

As this is a registry designed to determine outcomes for particular groups of patients, there will be more than one "primary" endpoint depending on the level of severity of illness. Knowing that survival in isolated VAD patients dominated by Profile I and II has reached 70% at one year, it is reasonable to assume that survival will be at least as good or better with VAD in less sick patients. We hypothesize that it will be possible to define baseline characteristics that predict a one year mortality of $\geq 35 \pm 5\%$ for patients on medical therapy and $\leq 25 \pm 5\%$ in patients who have had VAD. Seeking a confidence interval of approximately $\pm 5\%$, this could be accomplished initially with approximately 350 patients if they have similar risk. We anticipate that some patients will have better survival and some may have worse survival than this, such that there will be overlapping groups, and a small proportion of patients will have other events ending their medical history, such as transplant and deterioration to worse INTERMACS profiles for which they receive VADs.

For groups within which survival is > 60% at 1 year on medical therapy, a composite of survival and function will be the most important for comparison to VAD therapy. We hypothesize that it will be possible to identify a composite endpoint of survival and function that will show a 30% difference between outcomes on medical therapy and outcome with initial VAD. The nature of these survival-function endpoints will be explored during the first year of MEDAMACS data. The two simplest will be done with the endpoints of days alive out of hospital, and quality-adjusted life years according to the Euroqol. However, more complex endpoints will be tested for survival and functional scores at specific intervals. (Figure 5)

Information will be collected regarding the major adverse events that lead to hospitalization both with and without mechanical circulatory support, as listed in the data appendix: neurologic event, non-CNS bleeding, sepsis, ventricular tachyarrhythmia or ICD firing. The hospitalizations, adverse events and deaths will be attributed on site by the investigators in drop-down menus. There will be no independent adjudication of causes of hospitalizations or deaths. The general categories of causality are broad and not the focus of the primary hypotheses. Thus, the lack of formal adjudication should not compromise the data for the endpoints of death, transplant, and VAD, which are objectively determined. The secondary endpoints that relate to functional capacity and to quality of life will also be specifically determined.

Statistical Methods

Baseline data between different patient groups will be compared using student's t-test for normally distributed continuous variables and Wilcoxon Rank Sum for non-normally continuous variables. Kaplan-Meier curves will be constructed for time to death, VAD or transplant for the two-year study period. Event rates including cause-specific hospitalizations will be generated for different groups of patients and analyzed. Analysis plans for specific research questions will be developed under guidance of the DCC after approval by the Research and Publication Committee.

All summary statistics and subsequent analysis will be performed using SAS statistical software (Cary, NC).

Publications

Publications will be authored by the primary investigators at the participating sites. The senior site investigators will be offered inclusion as authors for the manuscripts on which they supervise the efforts of the investigator from their own site as first author. Options may become available for research coordinators to author manuscripts on secondary analyses of topics of their special interest.

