2. SPECIFIC AIMS

Aim 1: To identify prospectively a population of ambulatory patients followed on optimal medical therapy for whom chronic heart failure limits both function and survival to a range where elective implantation of left ventricular assist devices should offer meaningful benefit. *Hypothesis: It will be possible to define baseline characteristics that predict a one year mortality of* \geq 35±5% for patients on medical therapy and \leq 25±5% in patients who have had VAD.

- 1.1 Characterize ambulatory patients with advanced heart failure by baseline variables and interval change, including functional capacity, frailty, and interest in technical intervention. There will be two baseline measurements one month a part (used to predict early stability) and a repeated set at 1 year (used to predict outcome between 1 and 2 years). These outcomes will include: a). All clinical parameters required for current risk score models and prediction, b). Follow-up values and changes from baseline to 1 month and baseline to 1 year as additional variables from which to predict outcomes on medical therapy, c). Functional capacity, quality of life, and patient preferences at baseline and after time.
- 1.2 Distinguish between risk factors that predict mortality whether therapy is medical or mechanical, and those risk factors that predict outcomes with different impact depending on whether therapy is medical or VAD. This will be stratified by whether patient is eligible for transplant or not.
- 1.3 Record outcomes for ambulatory patients with advanced heart failure for comparison to VAD, to include a). Hospitalizations, VAD, transplant, survival without VAD or transplant, b). Major adverse events leading to hospitalization, including infection, neurologic or bleeding, c). Functional capacity and quality of life, d). Eligibility for transplant, e). Changes in resuscitation status and enrollment in hospice.

Aim 2: To design an integrated endpoint of survival and objective functional assessment that provides more discrimination between chronic ambulatory heart failure and current device outcomes than survival alone.

Hypothesis: It will be possible to identify a composite endpoint of survival and function that will show a 30% difference between outcomes on medical therapy and outcome with initial VAD.

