This chasm cannot be crossed by community registry populations which describe overall one-year mortality of 30-50%, but an average age is 75.^{9,10} with prevalence of co-morbidities such as chronic pulmonary disease and peripheral vascular disease in the range of 30%, with dementia, stroke, cancer each in the range of 10-20%.¹⁰ Multiple risk scores exist from these populations for the identification of patients at high risk for death from heart failure,¹¹⁻¹³ but they do not fully address the challenge of identifying ambulatory patients both sick enough and well enough to benefit from VADs. On the other end, scores developed from low-ejection fraction HF outpatient trials depict a young population with one-year survival rates in the range of 80-90%. In the pyramid of risk for death during heart failure, the largest level is the bed of risk at the base, in which the patient remains regardless of therapy received, with such risks as intrinsic liver and lung disease, and the intermediate levels where malnutrition and renal dysfunction compromise peri-operative outcomes and offer uncertain potential for improvement. (Figure 2) Potential for benefit is reflected best at the top of the pyramid with risk factors such as hemodynamics and biomarkers that are addressed directly by VAD (or transplant). The robust Seattle Heart Failure Score versions, derived from disparate trial populations, have been used to identify very low risk patients and patients with heart failure severity unlikely to benefit from ICD therapy.¹¹ This score will provide the central screen for the ongoing REVIVE-IT trial in ambulatory heart failure. The MedaMACS population is designed to surround the 50 patients on medical therapy in the REVIVE it trial, by including patients deemed sicker by recent hospitalization, but also less sick patients who have a Seattle score below the 1.5 threshold. The accuracy of current criteria to select this spectrum of patients has been shown in analysis of the first140 patients of the MedaMACS screening pilot. (Figure 3)

Functional Capacity Prediction

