Eligibility will be determined by the inclusion and exclusion criteria listed below. The inclusion criteria will be checked individually for "all that apply, with numeric values where indicated. The exclusion criteria will be verified by individual checkboxes. After determination of eligibility, a member of the study research team will approach individual subjects who are potential candidates for participation and for whom the subject's primary physician has given permission to approach. No group of persons will be excluded without a good scientific or ethical reason to do so. Incarcerated prisoners have been excluded by this protocol. For patients who meet inclusion criteria but who have an exclusion criteria related to non-cardiac conditions (Exclusion Criterion #2, #3, or #9) and for eligible patients not providing informed consent, a screening log will be kept that includes their age, ejection fraction, race and gender. This basic information is necessary to assess completeness of patient capture and possible bias in the screening process and in the process to obtain informed consent. No further information will be collected on patients who do not meet the inclusion criteria. This screening log will help determine the total number of advanced ambulatory heart failure patients eligible for MedaMACS participation at each study center.

We anticipate a total of 350 patients enrolled from 12 centers in the United States over a 12 month period. The screening pilot enrolled 168 patients at 10 sites during a 7 month period. Once all sites are activated with enrollment of approximately 3 patients per month per site, enrollment should be complete by 12 months.

Inclusion Criteria

- 1. Age 18-80 years
- 2. NYHA class III-IV heart failure for 45 of the last 60 days
- 3. Left ventricular ejection fraction $\leq 35\%$
- 4. Heart failure diagnosis or typical symptoms for 12 months
- 5. Use of evidence based oral medications (beta-blockers, ACE-inhibitors/ARBs, aldosterone antagonist) for at least 3 months prior to enrollment or documented medication contraindication or intolerance.

- 6. Hospitalization for heart failure within the previous 12 months (other than for elective procedure)
- 7. Informed consent given

In addition, they must have at least one of the following:

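### Does the ±5-point precision behind 350 patients mislead, given that the hypothesis is about a smaller group defined at baseline?

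*Combined protocol and SAP*

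**What the plan says.** The sample-size reasoning is in Section 8, under the heading on the primary endpoint and power. It hypothesises one-year mortality of at least 35 ± 5% on medical therapy and at most 25 ± 5% after VAD, seeks an interval of roughly ±5%, and concludes that "this could be accomplished initially with approximately 350 patients if they have similar risk". No confidence level is given. The next sentence warns that "some patients will have better survival and some may have worse survival than this, such that there will be overlapping groups", and adds that "a small proportion of patients will have other events ending their medical history", with transplant and VAD as its examples.

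Section 5 fixes the total: "We anticipate a total of 350 patients enrolled from 12 centers in the United States over a 12 month period". Aim 1 in Section 2 words the hypothesis in terms of a group to be identified: "It will be possible to define baseline characteristics that predict a one year mortality of" at least 35 ± 5%. Section 3 (Survival Prediction) says that the cohort takes in sicker patients "but also less sick patients who have a Seattle score below the 1.5 threshold".

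Section 8 also describes the analysis as descriptive and correlative, and states its purpose: "The intent is to identify a range of baseline profiles for which anticipated outcome with medical survival can be projected". For the comparison with VAD it adds a further rule. "For groups within which survival is > 60% at 1 year on medical therapy", a composite of survival and function takes precedence.

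**The concern.** The number that gives ±5 points is the same as the number to be enrolled. The stated precision therefore uses every patient as one group and leaves nothing over for subgroups or losses. Yet the hypothesis is about a group defined by baseline characteristics, and the plan expects the cohort to be mixed: less sick patients are admitted by design, and in Figure 3 90 of the 140 screening-pilot patients had a Seattle score below 1.5. No size or precision is given for any group smaller than the cohort.

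If a reader took ±5 points to describe the high-risk group, the registry would look more informative than it can be. The hypothesised gap between medical therapy and VAD is 10 points (35% against 25%), so a half-width of 8 to 10 points on the medical side would matter when target populations for later trials are chosen.

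**Working it through.** **Inputs.** Mortality p = 0.35 and half-width d = 0.05 (Section 8); n = 350 (Sections 5 and 8). Assumed: a two-sided 95% level, z = 1.96, because none is stated.

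**1. The plan's figure.** n = z²p(1−p)/d² = 1.96² × 0.35 × 0.65 / 0.05² = 349.6, so 350. At a 90% level (z = 1.645) the same formula gives 246.2, so 95% is evidently what was meant. The sum reproduces.

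**2. Does mixed risk break it for the whole cohort?** Half-width = 1.96 × √(p(1−p)/n), with n = 350:

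| Cohort mortality | Half-width (points) |
|---|---|
| 25% | ±4.5 |
| 35% | ±5.0 |
| 50% (widest possible) | ±5.2 |

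An illustrative mixture: 125 patients at 35% and 225 at 15%. Cohort mortality is (125 × 0.35 + 225 × 0.15)/350 = 22.1%, and the half-width is 1.96 × √(0.2214 × 0.7786/350) = ±4.35 points. The 125 and 225 are the pilot's 50/140 and 90/140 applied to 350; the two mortalities are assumptions. Heterogeneity does not widen the pooled interval. What it changes is the meaning of the pooled rate, which is then not the rate in the high-risk group.

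**3. A smaller group at 35%, estimated directly.** The protocol names no subset, so these sizes are illustrations only.

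| Group size | Share of 350 | Half-width (points) |
|---|---|---|
| 175 | one half | ±7.1 |
| 125 | 36%, the pilot share with a Seattle score of 1.5 or more | ±8.4 |
| 88 | one quarter | ±10.0 |

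**4. Losses to transplant or VAD.** The protocol gives no number. If 10% of the one-year information were lost, n = 315 and the whole-cohort half-width is ±5.3; if 20%, n = 280 and it is ±5.6. These treat the loss as a simple reduction in n.

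**5. The rule for survival above 60%.** Mortality of 35% is survival of 65%, so a group at exactly the hypothesised level already falls under that rule. The rule therefore does not mark the 35% group off from lower-risk patients. It also makes the survival-function composite, not mortality alone, the leading comparison with VAD for that group.

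**The case for a change.** The best argument for a change is that in a descriptive study precision is the main justification for the sample size. To state a condition, expect it to fail and print no consequence leaves the only mortality precision in the plan inapplicable to the group in the hypothesis. Section 2 (item 2.4) also wants the integrated survival-function results to inform patient decisions, guideline evidence and the size of later randomised trials. A sentence on subgroup precision would cost nothing.

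Part of this stands. The ±5 points is a whole-cohort figure, and a direct estimate for a smaller group at 35% will be wider. But the protocol does not say otherwise: the condition and its likely failure sit in adjacent sentences, so a reader is not misled about what the figure covers. Any subgroup figures added now would rest on group sizes that the plan does not define and on mortalities by risk group that the documents do not report. Nor is direct subgroup estimation the only route. Section 8 plans comparison with established risk scores and the building of new models, and it leaves analysis plans for specific questions to the coordinating centre after committee approval. Models that use all 350 patients may give narrower intervals than those in step 3.

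The VAD side adds little. By the same formula, ±5 points at 25% needs 1.96² × 0.25 × 0.75/0.05² = 288.1 patients. They would come from INTERMACS, a separate registry, and the documents do not say how many comparable patients it holds, so no shortfall can be shown.

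**Conclusion.** No change is needed. The 350 is the correct 95% figure for ±5 points at 35% mortality, and the plan attaches the right caution to it. For the whole cohort the precision is robust: ±4.5 to ±5.2 points for mortality between 25% and 50% before losses, and ±5.3 to ±5.6 at 35% if 10 to 20% of the information is lost (assumed). For a smaller group estimated directly at 35%, about ±7 to ±10 points should be expected with between 175 and 88 patients. That is a property of the group size and not an error in the plan. No decision rule, enrolment target or analysis depends on ±5 points holding in a subgroup, and every published interval will show the precision actually reached. A sentence confining ±5 points to the full cohort would be harmless but would change nothing that the registry does or concludes. This rests on a 95% level having been intended and on the registry being used as Section 8 describes it, to generate hypotheses.

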A final face to face encounter at 24 months (between 22-26 months) will be completed and the study will end at that point. Routine clinical assessment components and other study data elements will be recorded as available from the clinical record, including results of imaging and exercise testing for measurement of peak oxygen consumption, if performed at or after the 18 month time point. The six minute walk functional test will be repeated along with 5 meter gait speed to assess frailty. Patients will be re-administered the questionnaires regarding functional status, quality of life, and preferences for VAD as at baseline. Finally, at 24 months each patient

will receive the VAD survey and questionnaire to assess quality of life and perception of VAD technology. After the two year face to face visit, study participation will end.

Data Elements

A full list of data elements to be collected along with collection times may be found in Appendix B. All data will be recorded in a web based data entry system.

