of ala	limited	quite a bit	limited	limited	limit at all	not do for other
reasons						
Hobbies, recreationa	1					
activities						
Working or doing						
household chores						
Visiting family or fri	ends					
out of your home						
Intimate relationship	S					
with loved ones						

Please place an X in one box on each line

Developed by John Spertus et al., Mid America Heart Institute, Saint Luke's Hospital, Kansas City, MO.

Part III: MedaMACS VAD Survey

Thank you for taking the time to fill out this short survey. We will be asking you several questions about your heart failure and a new therapy for heart failure. This survey should take no more than 15 minutes of your time. Your responses will remain confidential.

1. Based on how you feel today and what you know about your heart failure, what is your

best estimate of how much longer you have to live? (choose one)

- A. Less than 6 months
- B. Between 6 months to 2 year
- C. Between 2 to 5 years
- D. More than 5 years

Ventricular Assist Device

There are many effective medical therapies available to treat congestive heart failure. Sometimes the heart can become too weak to pump enough blood to the body. At that stage, drugs may not be enough to treat heart failure.

Mechanical heart pumps called ventricular assist devices, or VADs, are a way to improve the circulation of blood throughout the body. These pumps do not replace the heart. They only assist the heart in pumping blood to the body. Once blood flow is improved, many patients have more energy and breathe easier. Clinical studies show that select patients with severe heart failure live longer with an assist device than with drug treatments alone.

Placement of a VAD requires major open heart surgery. The pump is placed inside the chest and abdomen and is connected to the heart. The VAD also has a power line that leaves the body through the skin in the front of the abdomen and is attached to a power supply outside the body. On average patients will remain in the hospital for about one month after surgery. Once discharged from the hospital, most patients are able to return home and live independently.

2. Based on how you feel right now and knowing only the above information above,

which statement best describes how you would feel about having an assist device placed?

- A. I would DEFINITELY want it
- B. I would PROBABLY want it
- C. I don't know if I would want it or not

- D. I would PROBABLY NOT want it.

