Alanine aminotransferase/SGPT B-type natriuretic peptide (BNP) NT-pro-BNP Metabolism Total cholesterol Low density lipoprotein High density lipoprotein Triglycerides Uric acid C-reactive protein Pre-albumin Albumin Hematologic White blood cell % lymphocytes	x x x x x x x x x x x x x x x x x			X X X X X X X X X X X X X		X X X X X X X X X X X X X
Alanine aminotransferase/SGPT B-type natriuretic peptide (BNP) NT-pro-BNP Metabolism Total cholesterol Low density lipoprotein High density lipoprotein Triglycerides Uric acid C-reactive protein Pre-albumin Albumin Hematologic White blood cell % lymphocytes Hemoglobin	x x x x x x x x x x x x x x x x x x x			X X X X X X X X X X X X X		X X X X X X X X X X X X X
Alanine aminotransferase/SGPT B-type natriuretic peptide (BNP) NT-pro-BNP Metabolism Total cholesterol Low density lipoprotein High density lipoprotein Triglycerides Uric acid C-reactive protein Pre-albumin Albumin Hematologic White blood cell % lymphocytes Hemoglobin Hematocrit	X X X X X X X X X X X X X X X X X X X			X X X X X X X X X X X X X X X		X X X X X X X X X X X X X X X
Alanine aminotransferase/SGPT B-type natriuretic peptide (BNP) NT-pro-BNP Metabolism Total cholesterol Low density lipoprotein High density lipoprotein Triglycerides Uric acid C-reactive protein Pre-albumin Albumin Hematologic White blood cell % lymphocytes Hemoglobin	x x x x x x x x x x x x x x x x x x x			X X X X X X X X X X X X X		X X X X X X X X X X X X X

QOL/PREFERENCES	Baseline A	Baseline B	6m	12m	18m	24m
EuroQoL	х	x	x	x	х	х
Thermometer	х	х	х	х	х	х
5 functional domains	х	х	х	х	х	х
Kansas City Cardiomyopathy	v	V		v		V
Questionnaire	X	X		X		X
Patient VAD survey instrument	X	X		X		X
Missing data survey	X Baseline	X Baseline		X		X
EVENTS/OUTCOMES	Α	В	6m	12m	18m	24m
Death		Х	Х	Х	х	Х
Primary cause of death (assigned by PI)		Х	Х	Х	х	Х
Sudden death		Х	х	х	х	х
Transplant		Х	Х	Х	х	Х
Listed for Transplant		Х	Х	Х	х	Х
Listing status		Х	х	х	х	х
VAD, if yes then		х	х	х	х	х
Type of circulatory support		Х	Х	Х	х	Х
Device name		Х	х	х	х	х
Intended Support Strategy Other Cardiac Procedure/Surgery		x		х		x
(name)		Х		Х		Х
Chronic inotrope infusion		Х		Х		Х
Resuscitation (Code) Status		Х		Х		Х
Hospice		Х		Х		Х
Recovery of EF to ≥40%		Х		Х		Х
Current NYHA Functional Class		Х		Х		х
Current INTERMACS Profile		Х		Х		Х
Hospitalization, reason for admission		Х		Х		Х
Heart failure with iv diuresis or inotrope		Х		Х		Х
Neurologic event		Х		Х		Х
Major bleeding (non CNS)		Х		Х		х
Transfusion		Х		Х		Х

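### The data plan does not reliably support the two named survival-function composites: Appendix B lists no hospital days, and the Euroqol schedule differs between sections

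*Combined protocol and SAP*

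**What the plan says.** Section 8, on the primary endpoint and power, gives one precision statement. For one-year mortality of 35% on medical therapy, a confidence interval of about ±5 points is sought, and "this could be accomplished initially with approximately 350 patients if they have similar risk". It then says that in groups with medical survival above 60% at one year "a composite of survival and function will be the most important for comparison to VAD therapy", and it hypothesises that one can identify a "composite endpoint of survival and function that will show a 30% difference between outcomes on medical therapy and outcome with initial VAD". The form of the composite is to be explored during the first year of data. Two versions are named as definite: "The two simplest will be done with the endpoints of days alive out of hospital", followed by Euroqol quality-adjusted life years. More complex endpoints are to be tested as well.

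On data collection, Section 6 (Data Elements) states: "A full list of data elements to be collected along with collection times may be found in Appendix B". The hospitalization entry under Events/Outcomes in Appendix B reads "Hospitalization, reason for admission", followed by a list of causes. Section 6 (telephone contact) has patients recall how many hospitalizations they have had, with major events confirmed from the record.

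On Euroqol, Section 6 (Patient Survey) and Appendix A Part II place the questionnaires at Baseline A, Baseline B, 12 months and 24 months. The telephone section lists functional class, profile, resuscitation and VAD preferences, and medications, but not Euroqol. Appendix B (QOL/Preferences) marks Euroqol, with its thermometer and five domains, at all six time points.

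**The concern.** The composite is not a side endpoint. The 35% mortality used to size the registry is 65% survival, so the registry's own planning population falls under the rule that puts the composite first. The 30% difference is also the Aim 2 hypothesis, and Aim 2.4 would use these endpoints to inform patient decisions and to size pivotal trials.

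Days alive out of hospital needs the number of days each patient spends in hospital. A count of admissions with reasons does not give that. Quality-adjusted life years need utilities at known times, and sites reading different sections would collect them at different times. Stay lengths might be recovered later from records with effort. A 6-month utility that was never asked for cannot be recovered. Because the form of the composite is to be explored during the first year, the inputs are needed from the first patient.

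**Working it through.** **1. The plan's own figure.** Inputs from Section 8: p = 0.35, half-width 0.05. The 95% level is my assumption. n = 1.96² × 0.35 × 0.65 / 0.05² = 349.6, so 350 reproduces. It is a precision figure for a mortality proportion and says nothing about a composite.

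**2. Does the composite rule apply at the planning point?** 1 − 0.35 = 0.65, which exceeds 0.60. It does.

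**3. Days alive out of hospital against the listed items.** Required: death date, and days in hospital per patient. Appendix B lists death without a date, and hospitalization by reason without a date or duration. It does list dates elsewhere: for echocardiography, right heart catheterization, ICD shocks and recent resynchronization implants. A date of death may be taken as implied, since Kaplan-Meier curves are planned. Length of stay is a separate quantity that nothing listed implies.

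**4. Euroqol under the two schedules.** Assumptions: 35% one-year mortality, deaths spread evenly, no missed visits, and no transplant or VAD before death. Baseline B is at day 42 (the late end of its 3 to 6 week window), the call at day 182 and the 12-month visit at day 365.
- Four visits: share dying after Baseline B with no later utility = 0.35 × (365 − 42)/365 = 31.0%. With Baseline B at day 21 it is 0.35 × 344/365 = 33.0%.
- Six time points: share dying after the 6-month utility and before month 12 = 0.35 × (365 − 182)/365 = 17.5%.

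For these patients the utility between the last measurement and death has to be assumed.

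**5. Illustration: how much hospital days matter.** Inputs: 35% and 25% one-year mortality with their ±5 ranges (Section 8), and a 30-day implant stay from the patient survey text in Appendix A Part III: "On average patients will remain in the hospital for about one month after surgery". No other hospital days are counted unless stated. Mean days alive in the year = 365(1 − m/2) for evenly spread deaths, or 365m/(−ln(1 − m)) for a constant hazard. Differences are VAD minus medical, relative to medical.

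| Case | Medical | VAD | Stay not counted | Stay counted |
|---|---|---|---|---|
| 1 year, 35/25, even deaths | 301.1 | 319.4 | +6.1% | −3.9% |
| 1 year, 35/25, constant hazard | 296.6 | 317.2 | +7.0% | −3.2% |
| 1 year, 40/20, constant hazard | 285.8 | 327.1 | +14.5% | +4.0% |
| 1 year, 30/30, constant hazard | 307.0 | 307.0 | 0.0% | −9.8% |
| 2 years, 35/25, constant hazard | 489.3 | 555.1 | +13.4% | +7.3% |
| 2 years, 40/20, constant hazard | 457.3 | 588.9 | +28.8% | +22.2% |

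The documents give no hospital-day rate on medical therapy. If it were 30 days per patient in the year (an assumption), with no VAD hospital days counted, the first row would become 319.4/(301.1 − 30) = 319.4/271.1, or +17.8%. So the unlisted quantity moves the result by more than the survival difference does, and at 35/25 over one year the treatment of the implant stay alone changes the sign.

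**The case against.** A reader might infer from the table that the plan's 30% hypothesis fails, since days alive out of hospital at 35/25 runs only from about −4% to +7% at one year. The documents do not support that. Section 8 attaches the 30% to a composite still to be identified, not to this candidate, and keeps more complex endpoints open. The −4% to +7% is also narrow by construction. It fixes one year and the two point values and ignores hospital days on medical therapy, in a cohort that can qualify through repeat hospitalization. Across the ±5 limits the range is about −10% to +14.5%, and two years at 40/20 reaches +28.8% without the stay. The one-month stay is lay survey text, not a planning input. Section 8 also points to Figure 5, which is not reproduced, so it cannot be said that no horizon was set. All of this stands, and it is no ground for excluding the endpoint from the planned exploration.

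On data items, Appendix B is not a field-level form: it gives no dates for death, transplant or VAD either, and record review is provided for. That excuses missing event dates. It does not supply a duration of stay. On Euroqol, the reason given for restricting surveys to face-to-face visits is help with the VAD portion, Section 6 names Appendix B as the source for collection times, and Section 4 reports that telephone outcome measures were being field-tested. Six time points may well be intended, but a site following Appendix A and the telephone section would not collect them.

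Finally, the analysis is described as descriptive, and detailed plans are deferred to the coordinating center. Deferring an analysis is reasonable. It does not help if the inputs are never collected.

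**Conclusion.** The point holds as a data-collection gap and an inconsistency, not as a numerical contradiction. As listed, the items do not allow days alive out of hospital to be computed, and the utilities behind the quality-adjusted life years depend on which section a site follows. The difference between schedules is about 31% versus 17.5% of patients, resting on 35% mortality, evenly spread deaths and the visit days above; the two percentages count deaths over different intervals after the last utility. The days-alive figures are illustrative only. They show that hospital days, and the handling of the implant stay, can decide the size of this composite and at one year its sign. The mortality estimate and its ±5 points are unaffected. This is a cheap improvement.

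**What to change.** - **Appendix B, Events/Outcomes:** add admission and discharge dates, or length of stay, for each hospitalization. Check that INTERMACS holds the same item, since the comparison needs it on both sides.
- **Euroqol schedule:** reconcile Section 6 (Patient Survey and telephone contact), Appendix A Part II and Appendix B. If telephone administration is intended, keep the 6 and 18 month assessments in Appendix B and add Euroqol to the telephone list and the Appendix A heading.
- **Section 8, endpoint:** report days alive out of hospital both with and without the implant stay.
- **Section 8, precision:** state that 350 patients and ±5 points refer to mortality only.

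The cost is a few sentences, one or two fields per hospitalization, and a short questionnaire at calls already planned. The downsides are coordinator time to abstract stay dates and a possible difference between telephone and written Euroqol responses, which should be noted when they are combined.
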